8.1.5. Sensitivity Analysis

A sensitivity analysis on the primary endpoint of change from baseline in average sleep disturbance score at Week 12 will be carried out using an analysis of covariance model (ANCOVA) with data from multiple imputation (MI) on missing scores under an assumption of missing at random (MAR). Under this assumption, each missing score will be imputed 100 times and incorporated with non-missing data to form 100 complete datasets. Each dataset will include average sleep disturbance score at Baseline, Week

4, Week 8, and Week 12, as well as relevant covariates specified below to support the analysis. Following steps will be conducted for this analysis. The number of imputations (100) will be informally verified by replicating sets of 100 imputations and checking whether the combined results are stable. If not stable, the number of imputations will be increased and informally checked as above, until stable estimates are obtained.

- Use the Markov chain Monte Carlo (MCMC) method to impute for intermittent missing values by study intervention group and to create 100 datasets with monotone missing pattern. According to the nature of sleep disturbance score, minimum and maximum values will be specified in this imputation.
- For each of 100 datasets with monotone missing pattern created from MCMC imputation, use monotone regression method to impute the remaining missing value by study intervention group up to Week 12. In the imputation regression model, age, BMI, stratum (Eastern Europe with high ICS dose, Eastern Europe with medium ICS dose, rest of world [ROW] with high ICS dose and ROW with medium ICS dose), inclusion in [REDACTED], baseline ACQ-5 score, and baseline sleep disturbance score, will be included as covariates. Change from baseline in sleep disturbance score at Week 12 can be calculated with non-missing score or imputed score for every single participant in all datasets. All 100 datasets with full imputation for missing values will be input to ANCOVA models.
- Repeatedly perform ANCOVA modeling for each of 100 datasets with full imputation for missing values. Change from baseline in sleep disturbance score at Week 12 will be analyzed on the ITTp population in this ANCOVA model, and study intervention (Dupilumab, Placebo), age, BMI, stratum (Eastern Europe with high ICS dose, Eastern Europe with medium ICS dose, rest of world [ROW] with high ICS dose and ROW with medium ICS dose), inclusion in [REDACTED], baseline ACQ-5, and baseline sleep disturbance score as covariates.
- The adjusted LS means in change from baseline of each study intervention group, the LS mean difference between the dupilumab and placebo groups, and the corresponding SEs and 95% CI of the differences generated from the 100 ANCOVA models will be combined using Rubin's formula and presented in a statistical table for the ITTp population.

8.1.6. Supplementary Analyses

As a supplementary analysis, the primary analysis will be replicated for the ITT population to investigate the robustness of the results.

Similarly, the primary analysis will be repeated for the ITT population but excluding the first 19 randomized participants, who were accidentally potentially unblinded to study team due to an issue with Interactive Response Technology (IRT), where study intervention arm was wrongly included in the IRT transfer to the IVRS library.

The primary analysis will also be repeated for ITTp population but setting to missing any assessment performed the night following a prohibited medication intake (whichever the prohibited medication and half-life of the product).

Lastly, the primary analysis will also be repeated for ITTp population but setting to missing any assessment performed after SCS intake.

8.1.7. Impact of Covid-19 Pandemic

During the Covid-19 pandemic, a business continuity plan (BCP) was put in place to minimize the impact of the clinic visit interruptions and ensure IMP treatment continuity and data collection. Direct to participant delivery of IMP from the site(s) and home injection(s) done by qualified site personnel and/or health care professionals for study drug administration were made available, where allowed by local regulations and approved by the participant, as planned per protocol. IMP permanent discontinuation due to Covid-19 pandemic is therefore expected to be minimum. Participant reported outcome data are not expected to be missing as they can be completed at the participant's home on his/her electronic devices. Site(s) can update/correct the schedule of completion if visit is rescheduled/delayed – unless site staff cannot access vendor platform to update scheduled dates.

Data missing due to the Covid-19 pandemic are likely to be MAR. Therefore, the primary analysis using MMRM can adequately address this type of missing data. Participant disposition summaries by visit according to trial impact (disruption) due to COVID-19 overall and by country are already mentioned in [Section 5.1](#) of this SAP.

8.2. Secondary and Tertiary/Exploratory Efficacy Endpoints

The secondary and tertiary efficacy endpoints associated with "Change from baseline" (except [REDACTED], due to limited sample size) will be analyzed using the MMRM model in the same fashion as for the analysis of the primary endpoint (see [Table 2-2](#)) with the baseline values corresponding to the outcome variables. Adjusted LS means for each study intervention group, LS mean difference between the Dupilumab and placebo groups, and the corresponding SEs and 95% CIs will be provided for all endpoints (and p-value corresponding to the LS mean difference provided at Week 12 only). However, formal statistical testing will be performed only for the number of nocturnal awakenings and PROMIS t-score that will be performed in the frame of the hierarchical procedure considered to account for multiplicity issues (nominal two-sided p-value provided for descriptive purpose only for other secondary and tertiary endpoints).

Further definitions of endpoints are included in [Section 15.8](#) and [Section 15.9](#).

8.2.1. Sleep diary

In addition to MMRM model, the number of nocturnal awakenings, sleep quality, restorative sleep, [REDACTED] WASO and [REDACTED], all based on sleep diary data, will be summarized at baseline and each post-baseline visit (Week 4, Week 8, and Week 12).

The number of nocturnal awakenings will be determined based on the answer on the question 3 from the sleep diary: "Approximately how many times did you wake up last night (not including when you woke up for the day today)?"

8.2.2. Actigraphy data

Duration and patterns of sleep (i.e., [REDACTED], WASO and [REDACTED]) will be estimated through a device (Actiwatch) worn on the wrist of the non-dominant hand of the participants, who will complete assessments from Day -11 to Day -1 (right before Day 1); daily assessment thereafter until Week 4; then only the week before a clinical visit until EOT.

In addition to MMRM model, all actigraphy parameters will be summarized through descriptive statistics at baseline and each post-baseline visit (Week 4, Week 8, and Week 12). WASO will be summarized separately to other actigraphy endpoints.

8.2.3. [REDACTED]

In addition to MMRM model, [REDACTED] will be summarized through descriptive statistics at baseline and each post-baseline visit (Week 4, Week 8, and Week 12).

8.2.4. Spirometry

For spirometry endpoint (pre-BD FEV1), the MMRM model will also include sex and baseline height as covariates.

In addition to MMRM model, spirometry parameter will be summarized through descriptive statistics at baseline and each post-baseline visit (Week 4, Week 8, and Week 12).

8.2.5. ADSD and ANSD

For both ADSD and ANSD, only the overall score will be presented/assessed and it will be calculated using the average from the 6 items.

In addition to MMRM model, data will be summarized through descriptive statistics at baseline and each post-baseline visit (Week 4, Week 8, and Week 12).

8.2.6. [REDACTED]

In addition to MMRM model, [REDACTED] 1-item questionnaire will be summarized through descriptive statistics at baseline and each post-baseline visit (Weeks 4, 8, and 12).

8.2.7. [REDACTED] in sleep since starting the study intervention

For [REDACTED] endpoint, the MMRM model will not include baseline value and baseline-by-visit interaction, since no baseline assessment is performed through this questionnaire.

In addition to MMRM model, [REDACTED] in sleep 1-item questionnaire will be summarized through descriptive statistics at Weeks 4, 8 and 12.

8.2.8. PROMIS Sleep Related Impairment Short Form 8a

In addition to MMRM model, the PROMIS Sleep Related Impairment SF8a t-score and raw score will be summarized at baseline and each post-baseline visit (Week 4, Week 8, Week 12).

8.2.9. Asthma Control Questionnaire [REDACTED] and ACQ-5)

In addition to MMRM model, the [REDACTED] global score as well as ACQ-5 score (the mean of the responses to the first 5 questions from the ACQ questionnaire) will be summarized at baseline and each post-baseline visit (Weeks 4, 8 and 12).

ACQ-5 baseline value will be used as a covariate for all MMRM models in the study, except for [REDACTED]

8.2.10. [REDACTED]

[REDACTED] summarized through descriptive statistics only due to the limited sample size of the sub-study.

8.2.11. [REDACTED]

MMRM model will be performed for the [REDACTED] concept scores [REDACTED]
[REDACTED]). All individual scores should be assessed in

employed participants only, except [REDACTED] (from question 6) which is not related to work. It will be run as specified generally in the [Section 8.2](#) but without assessment at Week 8.

The [REDACTED] concept scores will also be summarized at baseline and each post-baseline visit (i.e., Week 4 and Week 12) through descriptive statistics.

In addition, the number and percentage of participants currently employed (yes/no) will be presented at baseline and each post-baseline visit (Week 4 and Week 12) alongside with the number of participants evaluated at those visits.

8.2.12. [REDACTED]

In addition to MMRM model, [REDACTED] total score will be summarized at baseline and each post-baseline visit (Week 4, Week 8, Week 12) through descriptive statistics.

8.2.13. Multiplicity issues

In order to handle multiple primary or secondary endpoints, the overall Type-I error will be controlled by the use of a hierarchical inferential approach:

- Statistical significance of the primary analysis at the 0.05 alpha level will be required before drawing inferential conclusions about first secondary endpoint
- Inferential conclusions about successive secondary endpoints will require statistical significance of the prior one.

Hierarchical testing will be performed in the same order as described below:

1. Change from Baseline to Week 12 in the Asthma Sleep Disturbance Questionnaire (primary endpoint)
2. Change from Baseline to Week 12 in the average number of nocturnal awakenings (first secondary endpoint)
3. Change from Baseline to Week 12 in PROMIS t-score

This fixed hierarchical approach will ensure a strong control of the overall Type-I error rate at the 0.05 level.

Additional endpoints (secondary or tertiary) that are not included in the hierarchical testing procedure will not be formally tested (i.e., nominal p-value provided for descriptive purpose only).

9. Safety Analysis

All safety results will be summarized using the Safety analysis set by actual study intervention group.

The observation periods include:

- The **pre-treatment** period is defined as the time from the signed informed consent date up to first administration of the IMP.
- The **treatment-emergent adverse event** (TEAE) period is defined as the time from the first administration of the IMP (on Day 1) to the last administration of the IMP + 84 days or until the participant switches to commercialized dupilumab or other biologics
- The **post-treatment** period is defined as the time starting 1 day after the end of the TEAE period up to the end of the study follow-up.

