## 9.5 INTERIM ANALYSES

An interim analysis (IA) in the study is planned for the purpose of [REDACTED] when approximately 50% of participants (approximately 130 participants from the ITTp population) would have completed Week 12 visit or discontinued the study. The sample size re-estimation is planned to mitigate risk of power loss, given the large variability of placebo effects observed in [REDACTED] [REDACTED] Interim analysis will be performed as follows:

- The sample size re-estimation will be performed based on the observed treatment effects at the time of IA. Sample size may be increased if conditional power falls into the promising zone. No additional IA will be performed in the case of sample size increase. The test statistic at the final analysis may be adjusted as appropriate and details will be specified in the SAP.
- There is no plan to stop trial early for superiority at the time of IA. In order to preserve the overall Type I error rate of 0.05 (2-sided), gamma family alpha spending function will be utilized.

The IA will be performed by an internal independent statistical team, who are separate from personnel involved in the trial conduct. An independent Interim Analysis Committee (IAC) consisting of two clinicians and one statistician will review the results and make decision if the sample size needs to be adjusted based on prespecified criteria. A detailed plan will be defined in the SAP, including the plan to describe the processes intended to control access to comparative interim results to preserve trial integrity. People involved in the conduct of the study (participants, Investigators, Study Team, and Project Team) will have no access to the IA results.

At the time of IA, the primary efficacy endpoint will be analyzed using the same method described in the primary endpoint section ([Section 9.4.2](#)). The analysis population for the IA will be approximately 130 randomized participants from the ITTp population. The analysis of the endpoints will use all the data collected for the analysis population up to the IA cut-off time.

The database lock for final analysis is planned based on the date when the last participant completes the Week 12 visit or discontinues from the study before Week 12. Analyses will be based on all data collected up to this database lock and will be considered as the final analysis in the CSR.

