A large variability of placebo effects was observed between 200 mg and 300 mg placebo arms from [REDACTED]. The current treatment effect assumption was based on 200 mg placebo and 200 mg dupilumab arm. The impact of large variability of placebo effects on study power will be mitigated by conducting an interim analysis (IA) (see [Section 12](#)), and the final sample size will be determined by sample size re-estimation procedure based on the observed treatment effect at the time of the IA. The sample size may be increased up to a cap of 520 total randomized participants (260 each arm).

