4.4.5. Display of Data Summary and Analysis

Continuous variables will be summarized using descriptive statistics, including the following: sample size (n), mean, standard deviation (SD), median, first quartile (Q1), third quartile (Q3), minimum and maximum for each study intervention group.

All mean, Q1, Q3 and median values will be formatted to one more decimal place than the measured value. SD values will be formatted to two more decimal places than the measured value. Minimum and maximum will be formatted to the same number of decimal places as the measured value.

95% confidence intervals (CIs) will be two-sided and displayed to the same level of precision as the statistic they relate to. If an estimate or a CI is not estimable, it will be presented as ‘NE’. If neither an estimate, nor its CI are estimable, it will be presented as simply ‘NE’, not displaying ‘NE’ twice.

The p-values will be two-sided and will be rounded to three decimal places. If a p-value is less than 0.001 it will be reported as ‘<0.001’.

Categorical and ordinal data will be summarized using the counts and percentages. When count data are presented, the percent will be suppressed when the count is zero in order to draw attention to the non-zero counts. A row denoted ‘Missing’ will be included in count tabulations for demographics, baseline characteristics and compliance to account for missing values. No percentages will be displayed on the ‘Missing’ rows and the percentages on the other rows will be based on the number of non-missing observations. Unless otherwise specified, the denominator for all other percentages will be the number of participants in that study intervention within the specific analysis set of interest. All percentages will be rounded to one decimal place. The number and percentage of responses will be presented in the form xx (xx.x), where the percentage is in the parentheses. When the numerator is equal to the denominator, the percentage should be presented as (100) instead of (100.0), unless otherwise specified.

All listings will be sorted for presentation in order of assigned study intervention arm, study center number, participant number and date of procedure or event.

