9.6. Other Safety Data

Not applicable.

10. Pharmacokinetics

Pharmacokinetic parameters are not evaluated in this study.

11. Pharmacodynamics

Pharmacodynamic parameters are not evaluated in this study.

12. Interim Analysis

An interim analysis (IA) in the study is planned for the purpose of [REDACTED] when approximately 50% of participants (approximately 130 participants from the ITTp population and $n_1 = 117$ evaluable participants) have completed the Week 12 visit or discontinued the study. The sample size re-estimation is planned to mitigate risk of power loss in the primary MMRM analysis described in [Section 8.1.1](#), given the large variability of placebo effects observed in [REDACTED]. The IA will be performed according to the [REDACTED] summarized as follows:

- Let \tilde{n}_2 be the incremental sample size between Stage 1 and Stage 2 (viz., up to and after the IA, respectively), and the cumulative sample size up to and including Stage 2 (final analysis) be $n_2 = n_1 + \tilde{n}_2$.
- The sample size re-estimation will be performed based on the

- [REDACTED]
[REDACTED]
[REDACTED]
No additional IA will be performed in the case of sample size increase. The test statistic at the final analysis will not be adjusted, since no sample size increase is planned if that [REDACTED]
- There is no plan to stop the trial early for superiority at the IA, and therefore the type I error can be preserved in theory. To implement a conservative analysis, an administrative alpha of 0.001 will be spent at the interim and 0.049 will be reserved for the final analysis.

13. Changes in the Planned Analysis

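### SAP 8.2.13 opens the testing hierarchy at 0.05, but SAP 12 reserves only 0.049 for that same final analysis

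*SAP*

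**What the plan says.** SAP 8.2.13 sets a fixed sequence: the sleep disturbance score (primary), then nocturnal awakenings, then the PROMIS T-score. Its first rule is "Statistical significance of the primary analysis at the 0.05 alpha level will be required before drawing inferential conclusions about first secondary endpoint". For the later steps it says only: "Inferential conclusions about successive secondary endpoints will require statistical significance of the prior one". No number is attached to steps 2 and 3. A separate closing sentence claims strong control of the overall error rate at 0.05.

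SAP 12 (Interim Analysis) plans no early stop for superiority and says type I error is in theory preserved. It then chooses a conservative split, so that "an administrative alpha of 0.001 will be spent at the interim and 0.049 will be reserved for the final analysis".

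Protocol 9.5 sets the overall two-sided rate at 0.05, says that "gamma family alpha spending function will be utilized", gives no parameter and no final level, and defers: "A detailed plan will be defined in the SAP".

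SAP 13 lists three changes: the averaging period for awakenings, COVID-19 discontinuations and the safety set. None concerns alpha, and none of the 21 addendum items does either. On display, SAP 4.4.5 says: "The p-values will be two-sided and will be rounded to three decimal places".

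**The concern.** The primary endpoint and the hierarchy are tested once, at the final analysis. For that one test the SAP gives 0.05 in the section that defines the decision rule and 0.049 in the section that allocates alpha. If the final p-value falls between the two, the plan does not say whether the trial succeeded or whether the two secondary endpoints may be formally tested. A threshold picked after unblinding would be post hoc.

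The display convention does not help: a p-value in that band prints as 0.049 or 0.050, so the reported value cannot show which side of 0.049 it lies on.

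The point does not assert that the interim look inflates the error of a final test at 0.05. Whether the sample size re-estimation affects type I error depends on a redacted rule and is outside this point.

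**Working it through.** **Inputs.** 117 evaluable per arm, 90% power, two-sided 0.05 and 10% dropout (SAP 4.1); 0.001 and 0.049 (SAP 12); 0.05 (SAP 8.2.13); interim at about half the participants, with 117 evaluable in total (SAP 12). SAP 4.1 also gives the cap: "The sample size may be increased up to a cap of 520 total randomized participants (260 each arm"). The assumed effect and SD are redacted, so the standardised effect is back-solved. All calculations use the normal approximation with 1:1 allocation and leave out any effect of the re-estimation.

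**1. The plan's own total.** 0.001 + 0.049 = 0.050, which matches the overall rate. With the level in 8.2.13, 0.001 + 0.05 = 0.051, which does not.

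**2. Critical values.** z(1 − 0.05/2) = 1.960; z(1 − 0.049/2) = 1.969.

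**3. Implied effect.** d = (1.960 + 1.282) × √(2/117) = 0.424 SD. The 90% power at 0.05 is therefore reproduced by construction. A t-based calculation gives 0.426 SD.

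**4. How often the rules disagree.** With μ = d√(n/2), the rejection probability is Φ(μ − c) + Φ(−μ − c). The disagreement probability is its value at c = 1.960 minus its value at c = 1.969.

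| | 117 per arm | 234 per arm (520 × 0.9 / 2) |
|---|---|---|
| Power at 0.424 SD, level 0.05 | 90.0% | 99.57% |
| Power at 0.424 SD, level 0.049 | 89.85% | 99.55% |
| Disagreement under the null | 0.10% | 0.10% |
| Disagreement at 0.424 SD | 0.15% | 0.01% |
| Largest disagreement | 0.34% (near 0.257 SD) | 0.34% (near 0.181 SD) |

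The 234 per arm assumes the same 10% dropout at the cap.

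**5. Joint level if the interim 0.001 counted as a chance to reject.** This uses a bivariate normal with correlation √t. Here t = 0.5 if the sample size is unchanged, and t = 117/468 = 0.25 at the cap.

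| Final level | t = 0.5 | t = 0.25 |
|---|---|---|
| 0.049 | 0.0492 | 0.0496 |
| 0.05 | 0.0502 | 0.0506 |

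The 0.049 level keeps the total within 0.05 in both cases. The 0.05 level exceeds it slightly, but only if the interim is a real rejection opportunity, which no readable passage provides.

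**6. Steps 2 and 3.** Protocol 9.5 describes the interim for the primary endpoint only: "At the time of IA, the primary efficacy endpoint will be analyzed using the same method" as the main analysis. Take a final primary level of 0.049, with steps 2 and 3 at 0.05. If the primary null is true, any false rejection needs the primary to be rejected first, so the error is at most 0.049 (0.0496 counting the interim 0.001). If it is false, the error is at most 0.05. Either 0.049 or 0.05 is therefore valid for steps 2 and 3, but one should be stated. Moving a step from 0.05 to 0.049 costs 0.34, 0.24 and 0.15 points at marginal power of 50%, 80% and 90%.

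**The case against.** The strongest reply is that the 0.05 in 8.2.13 is the overall rate and Section 12 says how it is divided. The wording does not support this. The overall rate has its own sentence at the end of 8.2.13, while the first rule attaches 0.05 to the primary analysis itself.

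A second reply has more force. Section 12 speaks of alpha being spent and reserved, and the protocol names a spending function. On that reading 0.049 is the error left to spend, not a p-value cutoff. Solving the same bivariate normal for a joint 0.05 after spending 0.001 gives a final nominal level of about 0.0498 at t = 0.5 and 0.0494 at t = 0.25. The disputed band would then be about 0.0002 to 0.0006 wide instead of 0.001, so the figures in the first table are upper values across the two readings. The level still differs from 0.05. The simple additive split, described in the SAP as conservative, favours 0.049, and 0.049 is safe under either reading.

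A third reply is that the split is compatible with the protocol: a gamma-family function with parameter about −7.78 spends 0.001 of 0.05 at t = 0.5, and part of Section 12 is redacted. That is fair. The link is absent only from the readable text, so this is missing detail and not part of the contradiction.

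It is also true that, with no early stop for superiority, the look itself does not inflate a final test at 0.05. It is true too that rounding is a display rule and that either level is valid for steps 2 and 3. These observations limit the consequence; they do not remove the conflict.

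**Conclusion.** The concern holds, as a minor one. Two unredacted sentences of the current SAP give different levels for the same confirmatory test, and no later text chooses between them. The rules disagree with probability 0.10% under the null, 0.15% at the effect implied by the sample size, and at most 0.34% at any effect. This is a decision-rule defect, not evidence of material type I inflation. The sizes rest on a back-solved effect, a normal approximation, a fixed sample size and 0.049 read as a nominal cutoff. The conflict itself rests on none of these.

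**What to change.** Before the final analysis:

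- In SAP 8.2.13, replace 0.05 with two-sided 0.049 for the primary endpoint, to match the only explicit split in the SAP. Keep the sentence on overall control at 0.05.
- In the same place, state the level for steps 2 and 3. Using 0.049 throughout is the simplest consistent choice; 0.05 would also control the family-wise error.
- Say that the unrounded p-value is compared with the threshold.
- Add one addendum line on how the 0.001/0.049 split relates to the gamma-family sentence in protocol 9.5.

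This changes one number and adds two short sentences and one addendum line. Primary power falls by about 0.15 points (90.0% to 89.85%). If 0.049 is also used for steps 2 and 3, each loses at most 0.34 points. No extra patients are needed.
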